TITLE: Evaluating effects of animal assisted therapy on anxious pediatric dental patients using objective physiologic measures and self-reports of stress

NCT NUMBER: NCT04708028

DOCUMENT DATE: March 20, 2024

TITLE: Evaluating effects of animal assisted therapy on anxious pediatric dental patients using objective physiologic measures and self-reports of stress

ABSTRACT:

A striking 50-80% of adults and 6-22% of children suffer from dental anxiety which leads to disruptive behavior during appointments and avoidance of regular dental care. Though routinely used, common pharmacological interventions (i.e. oral sedation, general anesthesia) for anxiety management carry risks of adverse effects including stress on the respiratory and cardiovascular systems, neurologic injury, and even death. Data from various healthcare settings show reductions in pain and stress indicators in patients after implementation of a therapy dog for appointments. However, few studies have explored the physiologic and subjective effects of AAT on pediatric dental patients undergoing invasive procedures. To address this gap in knowledge and explore the effectiveness of animal-assisted therapy (AAT) in pediatric dentistry, we will study the subjective and objective responses of patients undergoing operative dental procedures that include an injection.

Our central hypothesis is that children who interact with a therapy dog before their dental procedure will have significantly lower physiologic and subjective, self-reported responses to anxiety. We will test this hypothesis with the following aims: **We will measure the physiologic effects of animal assisted therapy on pediatric patients' stress levels** by analyzing salivary stress hormones (i.e. alpha-amylase and cortisol) during invasive dental procedures (primary aim). For supplemental aims, **we will measure participants' heart rate throughout the dental visit, will evaluate the patients' self-perceptions of pain and anxiety** using pre-, intra- and post-procedural validated scales to assess responses to AAT and **will analyze participants' behaviors using observational coding.** Data will guide the implementation of AAT as a non-pharmacological anxiety management tool in dentistry, with the goal of improving access to care and patient safety among anxious pediatric patients.

SPECIFIC AIMS:

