Dental anxiety is linked to avoidance behavior and an increased pain response during dental procedures.^{1,2} At this time, limited methods for non-pharmacological anxiety control exist. The burden of sedation dentistry comes with many risks and financial costs. Some serious unwanted side effects include compromise to the patient's respiratory drive, airway reflexes and airway patency, as well as the cardiovascular system.³ Sedation for anxiety control is also costly for the patient and healthcare system, with deleterious effects on access to care. **Dentistry is in need of anxiety control measures other than pharmacological sedation** to reduce the risk to patients, lower the cost of treatment and thus increase access to dental care. One promising approach is animal-assisted therapy (AAT) using a well-trained therapy dog. In medical settings, AAT has been implemented in various clinical situations and has been shown to help reduce pain and stress indicators in patients.⁴ Research into AAT as a non-pharmacological behavior management and anxiety reduction techniques in dentistry is limited as many publications are surveys⁵ with a low sample size and are not conducted in the pediatric and/or dental patient population.²

To explore the effectiveness of non-pharmacological anxiety-reduction approaches, we will study the effects of animal-assisted therapy (AAT) on pediatric patients undergoing invasive dental procedures that include an injection. The University of North Carolina has a unique opportunity to explore animal-assisted therapy because the dental school has a certified therapy dog. Our central hypothesis is that children who interact with a therapy dog before their dental procedure will have significantly lower physiologic and subjective responses to stress. We will test this hypothesis by following aims:

Primary Aim: We will measure the effects of animal assisted therapy on pediatric patients' stress levels by analyzing objective physiologic measures (salivary amylase and cortisol) during invasive dental procedures.

Supplemental Aims: We will measure participants' heart rate throughout dental visit, will evaluate patients' perceptions of pain and anxiety using pre-, intra-, and post-procedural surveys to assess the patients' subjective responses to animal-assisted therapy and will analyze participants' behaviors using observational coding.

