The proposed study will examine the effectiveness of animal-assisted therapy on pediatric dental patients from a subjective and objective perspective to guide implementation of AAT in pediatric dental settings for anxious patients.

BACKGROUND AND SIGNIFICANCE:

Dental anxiety (DA) negatively impacts oral health worldwide. A meta-analysis reviewing DA in patients ages 3-18 years-old found a prevalence of 23.9%.⁶ Many adults attribute their dental anxiety to an earlier, traumatic dental experience.³ In a survey of 1,420 subjects, 16.4% adults had dental anxiety with 50.9% reporting dental anxiety onset in childhood.⁷ Dental anxiety is linked to avoidance behavior and an increased pain response during dental procedures.^{1,2,8} Avoidance behavior can lead to increased complexity of dental treatments, increased costs and often tooth loss with more emergency visits, increased probability of infection, and in severe cases, even death.⁹ A parent's own dental anxiety can also present a barrier to their child's access to dental care.¹⁰

Behavioral management and anxiety control techniques are essential to improving a child's experience and to avoid a lifelong fear of dental procedures.¹¹ The American Association of Pediatric Dentists (AAPD) recommends the use of pharmacological and non-pharmacological techniques to provide dental care for children with DA.¹² Even when regularly and safely used, moderate and deep sedation as well as general anesthesia pose patient risks including compromise to respiratory drive, airway reflexes and airway patency, and the cardiovascular system.^{3,13} For this reason, pharmacological behavioral management is often met with resistance from parents.¹⁴ Moderate to deep sedation and general anesthesia for anxiety control is also costly for the patient and the healthcare system. In a review of Medicaid claims in North Carolina from 2011-2015, general anesthesia was used in 15.8 out of 1,000 cases and cost approximately \$16.7 million per year. Expenditures on general anesthesia for dental procedures continue to increase.¹⁵ At this time, limited methods for non-pharmacological anxiety control exist. A low cost, low risk alternative to sedation is needed for anxious pediatric dental patients.

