Dentistry is in need of anxiety control measures other than sedation in order to reduce risk to patients, lower the cost of treatment and increase access to dental care. The pediatric dental experience may be improved by the implementation of a therapy dog for anxiety, pain and behavior management. Our investigation will be the first to comprehensively assess physiological and psychological effects of AAT using a randomized controlled trial with a therapy dog intervention. If efficacious at anxiety, pain and behavior management, AAT will offer dental providers a non-invasive, low-risk approach to provide positive dental experiences, with the translational goal of reducing dental avoidance and its significant negative health sequelae.

EXPERIMENTAL DESIGN AND METHODS:

We have designed a cross-sectional prospective controlled trial assessing whether AAT (intervention with a therapy dog) impacts physiologic biometrics and perceptions of anxiety, pain and future expectations during a dental procedure in pediatric patients.

Screening for research participants includes searching the dental school graduate pediatric clinic schedule for potentially qualifying participants scheduled for operative or restorative dental treatment. Inclusion and exclusion criteria can be found in **Table 1**.

Table 1: Inclusion and Exclusion Criteria

Inclusion Criteria	Exclusion Criteria
Ages 7-17, male or female	Fear or allergy to dogs
Patient receiving treatment at UNC Pediatric Dental Clinic	Non-English and non-Spanish speakers
Parent and participant speak English or Spanish	Learning disability or a developmental delay
Able to comprehend and follow the requirement of the study	Medical history that complicates dental treatment
Frankl Behavioral Scale II, III, or IV	Xerostomia (dry-mouth)

This study has been approved by the UNC IRB (IRB Number: 19-1911; Title: Animal Assisted Therapy's Effects on Dental Patients)

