The research team calls to interview parents/caregivers of patients for enrollment criteria (**Table 1**). If a participant enrolls, he or she is assigned to a random weekday which determines the therapy animal's availability and will be either the active control group or the experimental AAT (dog intervention) group. The research team sets up a Go-Pro camera to film the visit and places the heart rate monitor (Shimmer or Polar device) on the patient's wrist in the pediatric clinic's consultation room. The participant is asked a standardized set of anxiety scale questionnaires: the Modified Child

Dental Anxiety Survey (MCDAS) and the Children's Fear Survey Schedule, Dental Subset (CFSS-SD). The child also rates their current pain level using Wong-Baker FACES (WBS), a numeric scale, and the visual analog scale (VAS). After the interview, the AAT intervention or control (i.e. coloring or sitting in silence) takes place for 3 minutes. The intervention group will interact with the therapy dog using a reproducible, standardized method. The handler will introduce the dog, and the participant pets the therapy dog, shakes her paw, gives her a treat, and then says goodbye in the clinic's consultation room. The control group will color a picture of a dog (active) or sit in silence (passive) for 3 minutes. C-DART database software will be used to record patient responses and guide the research visit in a structured manner. Following the intervention, the child is taken into the treatment room with the heart rate device still on his or her wrist, collecting objective physiological data. The GoPro camera will be taken into the treatment room, to provide for simultaneous video and physiological data collection. Salivary samples using salivettes will be collected at 4 timepoints during the visit, as described in **Table 1**. See **Figure 1** for treatment visit protocol.

[figure not shown]

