Figure 1: Overall Trial Design. Subject participation commences with consent and a pre-procedural survey. Subjects are randomized to a dog intervention or a control intervention (coloring or sitting in silence). The first baseline saliva sample S1 is collected, followed by the 2-minute therapy dog interaction for experimental participants (controls will sit in the room coloring for 2 minutes without a dog or sit in the room in silence). A second saliva sample S2 is collected 8 minutes later, after the intervention. The local anesthetic injection or insertion of handpiece will occur, followed by the third salivary sample S3 collected 8 minutes later to ensure sufficient time for variation in salivary biometrics. The dental procedure will continue and at the end of the visit participants will provide their last saliva sample S4 and fill out a post-procedure survey about their experience, perceived pain, anxiety and future expectations. Study participation concludes. Video (GoPro), skin galvanic response and heart rate data are continuously collected throughout the procedure. Salivary samples are processed for alpha-amylase and cortisol by the UNC Biobehavioral Lab (BBL).

Primary Aim: We will measure the physiologic effects of animal assisted therapy on pediatric patients' stress levels. Salivary alpha-amylase (sAA) functions as a digestive enzyme involved in the breakdown of glycogen and starch as well as part of the immune system by protecting the oral cavity from harmful microorganisms.³⁰ Salivary alpha-amylase increases in response to stress.³¹ In a study of 99 patients undergoing an invasive dental procedure, Jafari et. al presented evidence to support the dependability and objectivity of using sAA to measure the acute stress response in patients with dental anxiety.³²

Another physiological indicator of stress response that can be measured in the dental setting is salivary cortisol. The hypothalamic-pituitary-adrenal axis (HPA) is an important aspect of the endocrine system which leads to release of cortisol from the adrenal glands when the body is subject to physical or emotional stress.³³ As supported by the 2007 meta-analysis by Miller et. al exploring cortisol levels and stress, the use of salivary cortisol levels is well cited in the scientific literature to be a validated biomarker for stress.³⁴

To collect a saliva sample, the research team places a salivette in the mandibular vestibule for 5 minutes at the following timepoints:

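### The aims specify procedures with an injection, but eligibility does not require one and Figure 1 lets handpiece insertion start the S3 clock; the SAP also leaves the S1 saliva baseline unused

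*Combined protocol and SAP*

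**What the plan says.** **Which procedures.** The Abstract announces a study of "responses of patients undergoing operative dental procedures that include an injection", and the Specific Aims repeat this: "pediatric patients undergoing invasive dental procedures that include an injection". The Primary Aim sentence itself says only that the procedures are invasive.

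**Who can enter.** Under Experimental Design and Methods, staff search the clinic schedule for "potentially qualifying participants scheduled for operative or restorative dental treatment". The only treatment-related inclusion criterion in Table 1 is being treated at the clinic. No criterion mentions an injection or local anaesthetic.

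**When S3 is taken.** The Figure 1 caption reads: "The local anesthetic injection or insertion of handpiece will occur, followed by the third salivary sample S3 collected 8 minutes later". Table 2 counts the eight minutes from the dental procedure, without defining its start.

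**When pain is rated.** Under Supplemental Aims, the three pain scales are given before the intervention, straight after the injection, and again at the end. No alternative is given for a child who has no injection.

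**How it is analysed.** The SAP names a row mean test for ordinal items, a chi-square test for categorical data, and a bivariate comparison of outcome by therapy-dog exposure at the 5% level. It mentions no procedure type, no missing pain rating and no use of the S1 baseline.

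**Order of assignment and baseline.** On enrolment "he or she is assigned to a random weekday which determines the therapy animal's availability". The Figure 1 caption puts the survey first: "Subject participation commences with consent and a pre-procedural survey. Subjects are randomized to a dog intervention or a control intervention". S1 follows assignment in both accounts.

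**The concern.** The stated aim and the entry rules describe different sets of children. By naming handpiece insertion as an alternative trigger, the plan itself foresees visits in which the injection is not the stressor. Such a child can be enrolled and analysed, yet is not of the kind the aims describe, and the plan defines no pain rating for that child during treatment.

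S3 is the only saliva sample taken during the procedure, so it bears most directly on the primary aim. Its eight-minute lag is there to let the salivary markers respond. If some children are timed from the injection and others from the handpiece, S3 mixes stressors and lags, and the SAP has no term to separate them.

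The S1 issue is separate. A baseline value of each analyte is collected for every child, but the stated comparison does not use it.

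**Working it through.** **Setting the sections side by side**

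| Item | Child with an injection | Child with handpiece only |
|---|---|---|
| Within the stated aim | yes | no |
| Eligible under screening text and Table 1 | yes | yes |
| S3 time zero, Figure 1 | injection, or handpiece if also used (not said which) | handpiece |
| S3 time zero, Table 2 | start of procedure, undefined | start of procedure, undefined |
| Pain rating during the procedure | defined | none |

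The handpiece-only child has 2 of 3 pain-rating occasions, or 3 of 4 if the post-intervention interview is separate from the end-of-procedure one. S3 and S4 follow the stressor and can carry the mix; S1 and S2 precede it. That is 2 of 4 samples.

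**Size.** The documents give no sample size, SD, effect size or non-injected share, so there is no planned figure to reproduce. Every numerical input below is assumed.

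*(a) Variance from mixing stressors.* Let q be the share without an injection and d the difference in S3 response between the two stressors, in within-group SD. A two-component mixture adds q(1−q)d² to the variance, so the unadjusted arm difference has variance multiplied by 1 + q(1−q)d².

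| q | d = 0.25 | d = 0.5 | d = 1 |
|---|---|---|---|
| 0.10 | 1.006 | 1.02 | 1.09 |
| 0.25 | 1.01 | 1.05 | 1.19 |
| 0.50 | 1.02 | 1.06 | 1.25 |

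For example, 1 + 0.5 × 0.5 × 1² = 1.25. The formula treats children as independent.

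*(b) Loss of pain ratings.* Take an effect of 0.5 SD, two-sided 5% and 63 children per arm, which gives 80.1% power. If a share q has no rating, 63(1−q) per arm remain. Power is 75.9%, 70.9% and 51.0% at q = 10%, 20% and 50%. Restoring it needs 63/(1−q) = 70, 79 and 126 per arm.

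*(c) Using S1.* With S1-S3 correlation ρ, adjusting for S1 multiplies the variance by 1 − ρ². For ρ = 0.3, 0.5 and 0.7 this is 0.91, 0.75 and 0.51, a reduction of 9%, 25% and 49%. The unadjusted analysis then needs 1/(1 − ρ²) = 1.10, 1.33 and 1.96 times as many children for equal precision.

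*(d) Both together.* Two simulations (100 children, true effect −0.40 SD, q = 0.5, d = 1, ρ = 0.5) gave these variances relative to no stressor mix: unadjusted 1.25 to 1.27; adjusted for stressor 1.02 to 1.03; adjusted for S1 1.01 to 1.02; adjusted for both 0.76 to 0.79. Mean estimates stayed at about −0.40, so there was no bias.

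*(e) Risk of adjusting.* S1 comes after assignment. If anticipation of the dog lowers S1 by 0.2 SD in the dog arm, the adjusted estimate moves towards zero by 0.2ρ = 0.06, 0.10 and 0.14 SD. A true −0.40 would read −0.34, −0.30 and −0.26. The unadjusted estimate stays at about −0.40.

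**The case against.** Much of the opposing case stands.

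- **The pain rating does have one anchor.** A reader might infer that it has none. The plan names the injection and nothing else; the defect is only that this event does not exist for a child without one.
- **Figure 1 and Table 2 need not conflict on S3.** They agree if the procedure is taken to begin at the injection or handpiece. The caption goes on to say that the procedure continues after that event, which is compatible with this reading. What remains open is which event counts when a child has both. The drawing is not reproduced in the text available here and may settle that.
- **The event may be recoverable.** Visits are filmed alongside physiological recording, so the actual trigger and its time could be read off later. No section says how they would be used, and the actual event follows the intervention, so it is a less safe covariate than the planned procedure type.
- **The effect may be negligible.** If recruitment follows the aims, the non-injected share could be near zero. The 25% figure needs both assumed extremes at once.
- **The bivariate comparison is valid under fair allocation.** Ignoring S1 costs precision; it is not an error.

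Two stronger readings are not supported. One is bias. If the handpiece-only share differed between arms by 10 to 30 percentage points and the stressors by 0.5 to 1 SD, the arm difference would move by 0.05 to 0.30 SD (0.10 × 0.5 to 0.30 × 1). But the weekday is described as assigned at random, and no section links procedure type to weekday or arm. The other is that a title about anxious patients contradicts the eligibility rules, which set no anxiety threshold. The Specific Aims only express a hope to "guide implementation of AAT in pediatric dental settings for anxious patients", and no stated analysis or conclusion is restricted to anxious children.

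**Conclusion.** The mismatch between aim and eligibility is real and follows from the text alone. Children without an injection can be enrolled outside the stated aim and without a pain rating during treatment, and a child with both events has no stated S3 time zero. The consequence is a change in what the S3 and pain results cover, plus added variance of unknown and possibly small size (0.6% to 25% on the assumed inputs). It is not, by itself, bias in a fair arm comparison.

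The unused S1 value is a separate matter of efficiency: a variance reduction of 9% to 49% forgone if the S1-S3 correlation lies between 0.3 and 0.7, a range the documents neither support nor exclude. The variance figures in (a) and (c) also assume independent children, which assignment by weekday may not fully satisfy.

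Both should be changed. Neither invalidates the trial.

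**What to change.** **1. Reconcile the Abstract, Specific Aims, screening text and Table 1, Figure 1, Table 2 and the pain-rating paragraph.** The choice is the investigators'. Either align eligibility with the stated aim, or widen the aim to injection or handpiece. If the aim is widened, record the planned procedure type before the visit (for example at the schedule search), adjust the S3 and S4 analyses for it, and limit the post-injection pain analysis to children planned for an injection. In either case, state one time zero for S3, identically in Figure 1 and Table 2.

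**2. Fix the primary salivary analysis in advance:** regression of each analyte on arm, adjusted for that analyte's S1 value. Always report the unadjusted estimate beside it as a sensitivity analysis.

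The SAP should not let the estimator depend on whether S1 looks different between arms. Chance imbalance cannot be told from anticipation, and switching drops the adjustment just when chance imbalance makes it most useful. With no true effect, no anticipation and a switch at p < 0.05, a large-sample calculation puts the unadjusted test's false-positive rate among switched trials at about 10%, 19% and 33% for ρ = 0.3, 0.5 and 0.7, against 5% for the adjusted test.

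**Cost.** Wording changes in the sections named, one SAP paragraph and, if the aim is widened, one new data field. S1 is already collected. Aligning eligibility with the aim may narrow enrolment slightly. The statistical downside is the understatement under anticipation shown in (e), 0.06 to 0.14 SD for an assumed 0.2 SD shift; the accompanying unadjusted estimate would show it.

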Table 2: Timepoints for salivary data collection

Timepoint	Description
S1	Baseline (pre-intervention, in consultation room)
S2	Post-intervention (8 minutes after intervention)
S3	8 minutes into the dental procedure
S4	8 minutes after completion of the procedure at the end of the study visit

Supplemental Aims: We will measure participants' heart rate throughout dental visit, will evaluate patients' perceptions of pain and anxiety using pre-, intra-, and post-procedural surveys and will analyze participants' behaviors using observational coding.

The Shimmer 3 GSR+ and Polar are small wearable wrist devices that measure heart rate through the wrist, with Shimmer 3 GSR+ also measuring sweat response through sensors that are fastened to the fingers. The Shimmer/Polar device will be connected to the patient during the pre-procedural interview, dog or control intervention, and procedure, continuously collecting heart rate and/or galvanic skin response (GSR) data.

Because heart rate is known to reliably increase under acute mental stress, it is widely used in medical research to evaluate stress response.³⁵ The Galvanic Skin Response (GSR) is a biomarker that quantifies the small electrical current induced by sweat which is released when the body is under stress.³⁶ The most significant psycho-activity and concentration of the epidermal sweat glands is on the sole of foot and the palm of the hand, particularly on the volar surface of the finger tips.³⁶ In a study completed by Caprara et. al in 2003, GSR was linked to increased dental anxiety in patients before undergoing a root canal treatment.³⁷

The video of the procedure as well as the heart rate data and GSR from the Shimmer device is loaded on to an external hard drive. The video will be coded with established behavioral codes using the Noldus software. The HR and GSR data are reviewed for inconsistencies using MindWare software. Both software are on a computer located in the bio-behavioral lab (BBL). The salivettes are transferred in a temperature-controlled container to the BBL where they are analyzed by ELISA for salivary alpha-amylase and salivary cortisol.

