Pre-intervention and post-intervention interviews will include the Child Fear Survey Schedule-Subset Dental (CFSS-SD), and the Modified Child Dental Anxiety Scale (MCDAS) to rate anxiety. To rate pain, the Wong-Baker FACES Scale (WBS), a numeric scale, and Visual Analog Scale (VAS) will also be used. The three pain rating scales will be repeated immediately after the injection. At the end of the procedures, the research team will repeat the CFSS-SD and the MCDAS for anxiety. They will also ask the child to rate his or her pain level again using the WBS, numeric scale, and VAS.

Pictorial representation of pain response, like The Wong-Baker FACES Scale (WBS), are preferred by children to express their level of pain regardless of age.³⁸ The Modified Child Dental Anxiety Survey (MCDAS) and the Children's Fear Survey Schedule, Dental Subset (CFSS-SD) are valid and reliable questionnaires in rating a child's anxiety in the dental setting.³⁹

STATISTICAL ANALYSIS PLAN:

To evaluate the values obtained on the various surveys, a RH Row Mean test will be utilized to compare questions that have Likert scale / ordinal responses and a chi square test will be used for categorical data. A bivariate analysis will be performed to compare the treatment outcome relative to the main exposure, which is the presence of the animal assisted therapy. The significance level will be $P < 0.05$.

Bibliography

1. Lima, D. S. M. *et al.* Does previous dental care experience make the child less anxious? An evaluation of anxiety and fear of pain. *Eur. Arch. Paediatr. Dent.* **22**, 139–143 (2021).
3. Coté, C. J. & Wilson, S. Guidelines for monitoring and management of pediatric patients before, during, and after sedation for diagnostic and therapeutic procedures. *Pediatr. Dent.* **41**, 259–260 (2019).
4. Marcus, D. A. *et al.* Animal-assisted therapy at an outpatient pain management clinic. *Pain Med.* **13**, 45–57 (2012).

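### Heart rate may come from either of two devices with no assignment rule, and the only analysis that could apply to it uses neither the child's own baseline nor the device

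*Combined protocol and SAP*

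**What the plan says.** All references are to the combined protocol and SAP.

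- **Devices.** Under Experimental Design and Methods, the research team "places the heart rate monitor (Shimmer or Polar device) on the patient's wrist" before the questionnaires. Supplemental Aims says the device runs through the interview, the dog or control activity and the procedure, "continuously collecting heart rate and/or galvanic skin response (GSR) data". Sweat response is attributed to the Shimmer alone. Nothing says how the device is chosen, whether the choice is balanced by arm, or whether the two devices agree.
- **Figure 1 legend.** It says "skin galvanic response and heart rate data are continuously collected" during the procedure, without a device condition.
- **Data handling.** The "heart rate data and GSR from the Shimmer device is loaded on to an external hard drive".
- **Activities.** The dog group pets the dog, shakes its paw and feeds it a treat. Controls colour a picture or sit quietly. The period is 3 minutes in the visit description and 2 minutes in the Figure 1 legend.
- **Allocation.** A child is assigned to a random weekday, and the dog's availability that day sets the group.
- **SAP.** Survey responses have named tests ("To evaluate the values obtained on the various surveys, a RH Row Mean test will be utilized", with chi-square for categorical items). Beyond that, "A bivariate analysis will be performed to compare the treatment outcome relative to the main exposure". Heart rate and GSR are not named, and there is no baseline term, device term, time window or summary measure.

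**The concern.** Two things are at stake if the bivariate comparison is applied to heart rate as written.

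1. **Precision.** Children differ in their usual heart rate. A reading taken before the intervention on the same device can remove part of that variation, and the protocol already collects one. The SAP does not use it.
2. **Device offset.** If the two devices read systematically differently and one is used more often in one arm, the offset becomes part of the arm difference. Because arm follows weekday, a device pattern linked to weekday would be enough.

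A whole-visit summary would also include the few minutes in which the arms are doing different things. GSR would be compared in whichever children wore a Shimmer, and their number by arm is not planned to be reported.

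**Working it through.** The documents give no sample size, SD, effect size, allocation ratio, device offset or device mix, so there is no figure to reproduce. The significance level of 0.05 is theirs (sidedness not stated; two-sided is used here). **Every other input below is an assumption for illustration.**

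**1. Precision forgone by not using the child's own baseline**

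Assume a true effect of 0.5 SD, 80% power and 1:1 allocation. With baseline correlation r, ANCOVA multiplies the residual variance by (1 − r²):

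n per arm = 2 × (1.960 + 0.842)² × (1 − r²) / 0.5²

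| r | n per arm |
|---|---|
| unadjusted | 62.79, so 63 |
| 0.3 | 62.79 × 0.91 = 57.1, so 58 |
| 0.5 | 62.79 × 0.75 = 47.1, so 48 |
| 0.7 | 62.79 × 0.51 = 32.02, so 33 |

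**2. Device offset left out of the comparison**

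Let b be the offset in bpm and Δp the difference between arms in the share of children on one device.

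- Bias = b × Δp.
- Variance = 144 + b² × (average of p(1 − p) over the arms), for a within-device SD of 12 bpm.
- The standard error is the square root of (variance × 2/n). The type I error follows from a two-sided normal test with its mean shifted by bias/SE.

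With a 50/50 mix in both arms, Δp = 0 and bias is 0. The variance ratio is (144 + 4 × 0.25)/144 = 1.007 for b = 2, and (144 + 25 × 0.25)/144 = 1.043 for b = 5. The cost is therefore 0.7% to 4.3% of variance.

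With unequal mix:

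| b (bpm) | Δp | Bias (bpm) | Type I error, 30 per arm | 50 per arm | 100 per arm |
|---|---|---|---|---|---|
| 2 | 0.2 | 0.4 | 0.052 | 0.053 | 0.056 |
| 5 | 0.2 | 1.0 | 0.062 | 0.069 | 0.089 |
| 2 | 0.5 | 1.0 | 0.062 | 0.070 | 0.090 |
| 5 | 0.5 | 2.5 | 0.125 | 0.176 | 0.305 |

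Worked example, b = 5, Δp = 0.5, 50 per arm: shares 0.75 and 0.25; variance 144 + 25 × 0.1875 = 148.7; SD 12.19; SE = 12.19 × √(2/50) = 2.44; shift 2.5/2.44 = 1.03; type I error 0.176.

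**3. Why a device term is needed as well as the baseline**

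A constant offset enters both the baseline and the outcome. After ANCOVA with slope β, about b × (1 − β) remains. If the two SDs are equal, β is about r, so at r = 0.5 roughly half the offset is still there. The baseline alone does not remove it.

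**4. GSR wording**

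The device text ties GSR to the Shimmer and says heart rate and/or GSR. The Figure 1 legend lists both streams with no condition. That the Polar records no GSR is the natural reading of the device text, though not stated outright. The legend therefore lacks a condition that the device text implies.

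**The case against.** The strongest reply is that a reader may take more from this than the documents contain.

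- **Pooling.** One might infer that the plan pools heart rate across devices and activities. It does not say so: it specifies no heart-rate analysis. Pooling is only what the bivariate comparison would do by default.
- **Calendar time.** One might infer that a change of device during the trial would confound the arms. With arm set by weekday, both arms would be expected to recruit in the same weeks, so a switch would fall on both about equally unless allocation also drifted. A device pattern linked to weekday would confound, but nothing in the documents suggests one.
- **GSR.** One might read Figure 1 as promising GSR for every child. The legend lists data streams, and the device text supplies the qualification. Nor does the transfer sentence show that Polar data are lost: it can be read as all heart-rate data, plus GSR from the Shimmer.
- **Movement.** Colouring also moves the hand, and the activity is a standardised 2 to 3 minutes of the visit. No figure for its effect is available.
- **Missing baseline term.** Under balanced allocation this costs precision and is not in itself an error.

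These replies stand, and they limit the point to what is left unspecified. They do not answer the absence of a device rule, or the failure to use a baseline that is already recorded.

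**Conclusion.** The point holds as a minor one, on a supplemental outcome. The plan allows two devices without an assignment rule, and the only analysis that could cover heart rate uses neither the child's own earlier reading nor the device.

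The precision loss does not depend on device imbalance. It depends on the baseline correlation, which the documents do not give: for correlations of 0.3 to 0.7, 33 to 58 per arm would do the work of 63. The bias is conditional on both an offset and a device mix that differs by arm. With balanced devices it is zero. For an assumed offset of 2 to 5 bpm and SD of 12 bpm at 50 per arm, type I error is 0.053 to 0.069 if shares differ by 20 points, and 0.070 to 0.176 if they differ by 50. These figures show the mechanism and do not estimate its size in this trial.

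For GSR, the fault is a legend lacking the Shimmer condition and an analysis subset that is never stated.

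**What to change.** 1. **Record the device** at every visit, state how it is chosen, and report its distribution by arm.
2. **Name one main heart-rate measure**, for example mean heart rate in the treatment room. Any event window should cover injection or handpiece insertion, since Figure 1 allows either. Treat other windows as secondary.
3. **Analyse it** by ANCOVA or a mixed model, adjusted for the child's interview heart rate before the intervention on the same device, and for device.
4. **Report the dog or colouring window separately and descriptively**, with the caveat that activity differs by arm. First reconcile its length (3 minutes in the visit description, 2 minutes in Figure 1).
5. **Limit GSR to Shimmer visits**, report their number by arm, and add the Shimmer condition to the Figure 1 legend.

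The cost is some SAP wording, one recorded variable and one or two degrees of freedom. There are two limits. The interview baseline is taken during anxiety questionnaires, so it is not a resting value; it still precedes the intervention and can serve as a covariate. And if device and arm turned out to coincide almost completely, no model could separate them, which is a further reason to state how devices are assigned.
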